Study Protocol and Statistical Analysis Plan

Study title: The Effects of a Single Dose of Wild Blueberries on Mood and Cognition in Healthy Young Adults: a Randomized, Double-blind, Placebo-controlled, Crossover Study

Date: 27 May 2021

1. Sample Size

A previous study with a similar crossover design found a significant effect of a blueberry drink intervention on mood using a sample size of 21 (Khalid et al. 2017). For the purpose of this study, we decided to include 30 participants – 15 male and 15 female, to be able to study the influence that sex might have on how the intervention affects our outcomes of interest.

2. Recruitment and Screening

Participants will be recruited using opportunity sampling. The study will be advertised online, through email distribution, and with posters across the University of Reading and the local community. Before interested participants are enrolled in the trial, we will invite them to the lab for a screening and familiarization session to determine if they meet the eligibility criteria, conduct a detailed baseline assessment of predictive factors, and give them an opportunity to become familiar with the cognitive task battery so as to reduce the influence of practice effects. Participants will be compensated with £100 (\$141) for completing the study.

3. Counterbalancing and Blinding Procedures

The participants will receive both interventions in a counterbalanced manner, i.e. half will be allocated to the order “blueberry → placebo” and the other half will receive the placebo first. The study will be double-blind. A researcher not involved in recruitment or data collection will prepare the intervention drinks and administer them in opaque shaker bottles. Thus, both participants and investigators will be blinded to the treatment assignment throughout the study.

4. Testing Protocol

Each participant will undergo two identical testing sessions at the Nutritional Psychology Lab. On testing days, participants will arrive at the lab after an overnight fast and will consume a standard breakfast of oat porridge. They will have been asked to follow a low-flavonoid diet on the day prior to testing. Next, participants will provide an intravenous blood sample and will complete the baseline cognitive task battery. When finished, they will consume the intervention drink they have been allocated to, prepared by mixing the blueberry or placebo powder with 250 ml water. Allowing 100 min for absorption, we will take another blood sample and will have participants repeat a different version of the same task battery.

5. Statistical Analysis Plan

The present study aims to investigate the acute (2 hours) effects of a wild blueberry intervention on mood and cognition in a population of healthy young adults. On the recommendation of a statistician, all repeated measures data will be analyzed in RStudio using linear mixed-effects models (LMMs). This technique can be used to model variance relating to both fixed parameters such as experimental doses and random parameters such as individual differences between subjects, within multiple layers of the same model. We will adjust the model for baseline variables, such as sex, fruit and vegetable consumption, physical activity level, alcohol use, and systemic inflammation, where the inclusion of these covariates improves the fit of the model. Subjects will be included as a random factor as a way of controlling for non-independence of data from the same subjects. Where possible, an unstructured covariance matrix will be specified for the repeated observations on a subject within the same period. As LMMs do not require balanced data, subjects with missing data points will not be excluded from the analyses.

References

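### Does the double-blind claim fail because Section 3 does not say whether the researcher who prepares and administers the drinks knows the allocation?

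*Combined protocol and SAP*

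**What the plan says.** Section 3 (Counterbalancing and Blinding Procedures) declares the level of blinding: "The study will be double-blind". It gives two safeguards in one sentence: "A researcher not involved in recruitment or data collection will prepare the intervention drinks and administer them in opaque shaker bottles". It then draws the conclusion: "Thus, both participants and investigators will be blinded to the treatment assignment throughout the study".

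The design is a two-period crossover: "The participants will receive both interventions in a counterbalanced manner", so that "half will be allocated to the order “blueberry → placebo” and the other half will receive the placebo first".

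Section 4 (Testing Protocol) adds the setting, "Each participant will undergo two identical testing sessions at the Nutritional Psychology Lab", and the only other mention of the powders: the drink is "prepared by mixing the blueberry or placebo powder with 250 ml water". In each session the first blood sample and the baseline battery come before the drink. The second sample and battery follow after 100 minutes.

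Neither section says whether the powders carry a code, who holds the allocation list, or whether the preparing researcher counts among the blinded investigators.

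**The concern.** The word that opens the conclusion in Section 3 presents blinding as a consequence of the two safeguards, but they cover only part of what is concluded. Keeping the preparer out of recruitment and data collection protects the outcome assessor. The opaque bottle hides the drink's appearance from the participant. Neither deals with what the person bringing the drink might convey if that person knows what is in it.

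Three features make the question fair here. First, a cue of this kind would be tied to the drink and not to the period, so counterbalancing the order would not remove it. Second, each participant receives both drinks, so identifying one identifies the other. Third, mood is a title outcome. If it is self-rated (an assumption, since the documents do not name the measure), it is the outcome most open to expectation, and the blood samples are the least open. If such a cue operated, the treatment contrast for mood could contain an expectation effect, and the double-blind label would claim too much.

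**Working it through.** The point has no stated figure to reproduce. The check is to set the two sections side by side and see what each possible reading implies.

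**Exposure.** Section 1 plans 30 participants and Section 4 gives two sessions each: 30 × 2 = 60 administrations. This is a maximum, reached only if everyone completes both sessions. It counts opportunities for a cue and does not measure bias.

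**Two readings of who is blinded.**

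1. *The preparer is one of the investigators.* The conclusion in Section 3 then says that this person is blind too. Only the means (coding, for example) is left out, and blinding is complete as declared.
2. *The preparer is outside that group and may know the allocation.* Separating this person from data collection is then the purpose of the arrangement. Assessors remain blind, and the participant cannot see the drink. The only uncovered route within this point is contact when the drink is given.

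The text does not contradict itself under either reading.

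**What bias would need under the second reading.** All four of these must hold:

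- the preparer knows the allocation;
- the preparer gives a cue;
- the participant notices it and reads it correctly;
- the belief shifts the scores.

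The documents neither support nor exclude any of these. They do not describe the contact, who else is present, or whether anything is said.

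**Timing.** In session 1 the baseline battery is finished before the drink, so a cue could reach only the post-dose scores. In session 2 a participant who had identified the first drink would already know the second, so both baseline and post-dose scores could move. The source of the bias would follow the drink, but its net effect on a baseline-adjusted comparison has no predictable size. No estimate is possible from the documents.

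**What a change would buy.**

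| Option | Effect | Limit |
|---|---|---|
| A sentence stating current practice | Lets a reader verify the claim | Changes neither the data nor the analysis |
| Coded powders, same researcher mixes and administers | Could blind the preparer | Works only if the mixer cannot tell the powders apart by sight or smell; the documents do not say so |
| An unaware person hands over a closed bottle | Does not depend on matched powders | Needs a further person outside data collection for up to 60 administrations |
| Asking participants to guess the order at the end | Documents belief | Protects nothing, and cannot separate a cue from taste or from a real effect |

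**The case for a change.** The strongest case for acting is that the omission is certain and the remedy is cheap. Both sections can be read in full without finding a word on coding or on the preparer's knowledge. The conclusion about investigators does not settle the matter, because it does not define the group. Separating the preparer from data collection makes most sense if that person may know the allocation, yet the same person then administers every drink. If coding is already in place, one sentence would let readers confirm the double-blind claim in the title.

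What stands is that the detail is missing and that a fuller account would be easier to verify. What does not stand is the step from there to a defect in the plan. That separation is an inference about motive and does not show that the preparer is unblinded. The one-sentence remedy documents practice and leaves conduct as it is. The remedy that would alter conduct at little cost, coding the powders, could give false assurance: a mixer who can recognise the powder does not need the code list.

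**Conclusion.** No change to the plan follows. Section 3 leaves out a detail of blinding procedure. It does not contradict itself, and nothing in Section 4 shows that blinding fails. The declared blinding, the separation of the preparer from recruitment and data collection, and the opaque bottles form a sensible arrangement, and a competent team carrying it out would settle how the powders are handled as ordinary practice.

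The exposure is at most 60 administrations. The resulting bias cannot be sized and may be nil. The possible importance for mood rests on the assumption that mood is self-rated, and any harm rests on the four unstated conditions set out above. The available changes either only record what is done, depend on an unstated property of the powders, or add a person at each session for an uncertain gain. The taste and smell of the drinks are a separate route to unblinding and do not bear on this conclusion.

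### The analysis plan names no session (period) fixed effect for this two-session crossover, although practice effects on the cognitive battery are an acknowledged concern

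*Combined protocol and SAP*

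**What the plan says.** The design is a two-period crossover: "Each participant will undergo two identical testing sessions at the Nutritional Psychology Lab" (section 4), and "The participants will receive both interventions in a counterbalanced manner" (section 3), half in each order. In each session the battery is taken before the drink, and afterwards the researchers "will have participants repeat a different version of the same task battery" (section 4). A screening visit lets participants get used to the battery "so as to reduce the influence of practice effects" (section 2).

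Section 5 describes the linear mixed model through four elements:

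- an illustration of what such models can contain: "fixed parameters such as experimental doses and random parameters such as individual differences between subjects"
- baseline covariates such as sex, diet, activity, alcohol use and inflammation, kept where they improve fit
- a subject effect: "Subjects will be included as a random factor as a way of controlling for non-independence of data from the same subjects"
- a covariance structure: "Where possible, an unstructured covariance matrix will be specified for the repeated observations on a subject within the same period"

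Session, period and order are not named as fixed effects. The single use of the word period defines a covariance block. It describes how scores within a session correlate and does not adjust their mean.

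**The concern.** Section 2 speaks of reducing practice effects, not removing them, and the battery is then taken four more times (two sessions x two batteries). If scores still drift between sessions, a model built only from the terms section 5 names leaves that drift in the error. The rule of keeping terms that improve fit covers baseline variables only, so nothing settles whether session enters.

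The consequence depends on the contrast, which section 5 does not state:

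- **Drink x time** (both batteries as outcomes): a constant session shift cancels. Only a difference between sessions in the practice gain matters.
- **Post-drink scores alone:** any remaining session shift inflates the estimated standard error, and the test loses power.

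Under either contrast, a small bias appears if losses differ by drink order. Another appears in the sex comparison that section 1 wants ("15 male and 15 female, to be able to study the influence that sex might have"), because 15 people of one sex cannot be split evenly between two orders. The point concerns the cognitive battery; the documents give no basis for expecting the same drift in mood.

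**Working it through.** **Inputs from the documents.** N = 30, 15 per sex (section 1); half in each order, so 15:15 (section 3); two sessions with a battery before and after the drink (section 4); participants with missing data retained (section 5). Section 1 gives no alpha, power, effect size or SD for the 30, so there is no plan figure to reproduce.

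**Assumptions.** Two-sided alpha 5%. The true effect is the one with 80% power when session is modelled; for post-drink scores this is 0.53 SD of the within-subject difference. All session-effect sizes are assumed.

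**1. Post-drink scores, session omitted.** Let k = session shift / SD of the within-subject difference (blueberry minus placebo). The shift enters that difference with opposite signs in the two orders. The mean stays unbiased at 15:15, but the residual sum of squares becomes noncentral chi-square with 29 df and noncentrality 30k². The SE ratio is sqrt(1 + k² x 30/29), and the information lost is 30 x (1 - 1/ratio²) participants. For k = 0.39: 0.1521 x 30/29 = 0.157, ratio 1.076, loss 30 x (1 - 1/1.157) = 4.1. Type I error and power come from numerical integration.

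| k | SE | Type I error | Power | Participants' information lost |
|---|---|---|---|---|
| 0.2 | +2.0% | 4.6% | 78.9% | 1.2 |
| 0.39 | +7.6% | 3.6% | 75.6% | 4.1 |
| 0.5 | +12.2% | 2.9% | 72.6% | 6.2 |

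With the session term, type I error is 5.0% and power 80.0% at every k. A simulation of 40,000 trials at k = 0.5 without the term gave 2.8% and 73.0%.

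**2. Drink x time, session terms omitted.** Take score variance 1 and within-session correlation 0.7. A pre-to-post change then has variance 2 x (1 - 0.7) = 0.6, and the difference between two changes has SD sqrt(1.2) = 1.095. A constant shift drops out of each change (SE ratio 1.000). If the practice gain differs by g between sessions, each change is displaced by g/2 about the average. With random subject plus a within-period covariance, the model treats the two changes as independent, so the large-sample SE ratio is sqrt(1 + (g²/4)/0.6). For g = 0.3: sqrt(1 + 0.0225/0.6) = 1.019.

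| g (SD) | SE | Type I error | Power |
|---|---|---|---|
| 0.1 | +0.2% | 5.0% | 79.9% |
| 0.2 | +0.8% | 4.8% | 79.6% |
| 0.3 | +1.9% | 4.6% | 79.0% |

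With within-session correlation about 0.5 to 0.6, the ratios are 1.002, 1.007 and 1.016. A paired analysis of the two changes is more sensitive: at g = 0.3, k = 0.3/1.095 = 0.274, the SE rises 3.8% and power is about 78%.

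**3. Unequal losses.** Suppose three people in one order miss session 2 and none do in the other. One drink then has 15 of 30 sessions in session 2, the other 12 of 27.

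- Drink x time: bias = 15/30 - 12/27 = 0.056 of g. At g = 0.3, 0.056 x 0.274 x sqrt(30) = 0.08 SE.
- Post-drink, generalised least squares: bias = 0.072, 0.083 and 0.094 of the shift at between-session correlation 0.3, 0.5 and 0.7. At k = 0.39 the range is 0.072 x 0.39 x sqrt(30) = 0.15 SE to 0.094 x 0.39 x sqrt(30) = 0.20 SE.

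Equal losses give zero bias. SEs here are for the full sample.

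**4. Sex comparison.** The nearest to an even split is 8/7 in one sex and 7/8 in the other. Each sex-specific effect is biased by (8 - 7)/15 = 1/15 of the session effect, in opposite directions, so the contrast is biased by 2/15.

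- Post-drink, k = 0.39: (0.39/15) x sqrt(15) = 0.10 SE, and (2 x 0.39/15)/sqrt(2/15) = 0.14 SE.
- Drink x time, g = 0.3: the same formulas with 0.274 give 0.07 and 0.10 SE.

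**The case against.** The strongest reply is that this is an unwritten term, not a wrong choice. Section 5 does not write out its fixed effects at all: time and drink x time are missing too, and the wording about doses is only an example. Nothing excludes a session term, and using period to structure the covariance suggests the authors had the crossover layout in mind. That stands as a description of the text. It leaves the choice open until the data are seen.

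The second reply is that a covariance for repeated observations within a period makes most sense if both batteries are outcomes. Drink x time is then the likelier contrast, and for it the loss is at most one percentage point of power in the range examined. This also largely stands. The larger losses apply only if post-drink scores alone are compared, which section 5 does not exclude. The two assumed ranges also differ in scale: with between-session correlation 0.7, k = 0.5 corresponds to 0.5 x sqrt(0.6) = 0.39 SD of the score, beyond the 0.3 SD examined for drink x time.

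Third, the design already helps through familiarisation, counterbalancing, a pre-drink battery in each session and a different version at the repeat. All of these limit the harm. However, the plan does not say how versions are assigned across sessions, and counterbalancing does not take session variance out of the error.

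Finally, putting session in every model reaches the mood outcomes, where no practice effect is documented. That is fair as to scope, but the extra term there is harmless.

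**Conclusion.** The concern holds and is minor. Section 5 names no session mean effect, and a model limited to the terms it names would leave any residual practice shift in the error. On complete, balanced data the overall drink effect is unbiased and the test is conservative, so a positive finding would not be undermined.

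The size depends on an unstated contrast and on session effects the documents do not give. For drink x time, power falls from 80.0% to no lower than 79.0% for gain differences up to 0.3 SD in the mixed model. For post-drink scores, it falls to between 78.9% and 72.6% for k from 0.2 to 0.5. The biases from unequal losses or the sex split are 0.07 to 0.20 SE at the values tried, small beside sampling error. If no session effect remains after familiarisation, nothing is lost.

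**What to change.** In section 5, state that every model includes drink and session (1 or 2) as fixed effects regardless of fit. Where pre- and post-drink scores are both outcomes, also include time, drink x time and session x time. Keep the rule that retains participants with missing data.

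The cost is one line of wording and 1 to 2 degrees of freedom. If there is no session effect, power for post-drink scores is 80.0% with the term and 80.1% without it; for drink x time it is 80.0% either way. Session number follows from the allocated order, so no new data are needed. The terms restore the correct standard error and remove the biases that an additive session effect causes through unequal losses or the sex split.
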